Placebo-controlled design was chosen because when they are utilized with randomization, they allow for valid treatment group comparisons. The disadvantage of parallel designs is that they can require large sample sizes due to the existence of both within- and between-subject variation. Cross over studies generally require fewer participants than parallel designs because each participant serves as his/her own control, thus eliminating inter-participant variation. Secondly, researchers can study individual participant response to treatment and examine participant-by-treatment interactions. Lastly, study recruitment may

be enhanced as potential participants are aware that they will receive active treatment at some point during the study.

[figure not shown]
c) End of study definition

End of study will occur once all participants have undergone both intervention and placebo arm of the study. Each subject will be enrolled for study period of 9 weeks.

6) Arms and Interventions

Study Arm Description

**FUNCTIONAL SUCRASE DEFICIENCY IN SHORT BOWEL SYNDROME PATIENTS
WITH INTESTINAL FAILURE**

Patients meeting inclusion criteria will be enrolled in the study and will provide written consent in keeping with regulations of the IRB.

Once enrolled “subjects” will be observed for 1 week on their current care and we will record:

Record daily:

Stool frequency and consistency

Side effects on sucrase – blood sugar checks by finger stick and any new symptoms – nausea, headache, etc

Emesis

Record weekly:

Ability to advance feeds

Abdominal circumference

Weight

Patient or parent perception of tolerance of feeds on sucrase by telephone questionnaire

**FUNCTIONAL SUCRASE DEFICIENCY IN SHORT BOWEL SYNDROME PATIENTS WITH
INTESTINAL FAILURE**

DAILY RECORD FOR EACH WEEK

	DAY 1	DAY 2	DAY 3	DAY 4	DAY 5	DAY 6	DAY 7
STOOL FREQUENCY							
STOOL CONSISTENCY							
SUCRASE SIDE EFFECTS							
HEADACHE (YES/NO)							
NAUSEA (YES/NO)							
ABDOMINAL PAIN (YES/NO)							
VOMITING (YES/NO)							
BLOOD SUGAR							

WEEKLY RECORD (EXCEPT WASH OUT WEEK)

	WEEK 1	WEEK 2	WEEK 3	WEEK 4
ABILITY TO ADVANCE FEEDS				
ABDOMINAL CIRCUMFERENCE				
WEIGHT				

	WEEK 6	WEEK 7	WEEK 8	WEEK 9
ABILITY TO ADVANCE FEEDS				
ABDOMINAL CIRCUMFERENCE				
WEIGHT				

**FUNCTIONAL SUCRASE DEFICIENCY IN SHORT BOWEL SYNDROME PATIENTS WITH
INTESTINAL FAILURE**

TELEPHONE QUESTIONNAIRE

	WEEK 1	WEEK 2	WEEK 3	WEEK 4	WEEK 6	WEEK 7	WEEK 8	WEEK 9

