Patient or parent perception of tolerance of feed on sucrase								

POSSIBLE ADDITIONAL TESTING

- Blood test for genetic testing if available.
- If scheduled for an endoscopy, for other medically indicated reasons as decided by the medical team, will have biopsies taken to rule out CSID.
- Breath test for functional sucrase deficiency in patients who consent.

Study Intervention Description

Subjects will be administered sucraind (sucrase) daily as instructed and followed as above. There will be a one week wash out period
During cross over subjects will be administered “placebo” daily as instructed and followed as above.

a) Intervention dosing and administration information

The recommended dosage is as follows: 1 mL (8,500 I.U.) (one full measuring scoop or 28 drops) per meal or snack for patients up to 15 kg in body weight. 2 mL (17,000 I.U.) Dosage

is 1 or 2 mL (8,500 to 17,000 I.U.) taken orally or by g-tube with each meal or snack diluted in water, milk, or infant formula. Half of the dosage will be taken at the beginning of the meal or snack and the remainder be taken during the meal or snack. The beverage or infant formula should be served cold or at room temperature. The beverage or infant formula should not be warmed or heated before or after addition of Sucraid because heating is likely to decrease potency.

b) Study Intervention Compliance

Patients will be called weekly for verification of compliance. Most patients have home nursing so their home nursing records will be reviewed as well. Finally patients will be asked to verify how much medication they have left at end of each week to assess compliance.

7) Procedures Involved

Patients meeting inclusion criteria will be enrolled in the study and will provide written consent in keeping with regulations of the IRB.

Once enrolled “subjects” will be observed for 1 week on their current care and we will record:
Record daily:

Stool frequency and consistency

Side effects on sucrase – blood sugar checks by finger stick and any new symptoms –
nausea, headache, etc

Emesis

Record weekly:

Ability to advance feeds

Abdominal circumference

Weight

Patient or parent perception of tolerance of feeds on sucrase by telephone questionnaire

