In the treatment arm of the study, subjects we will give sucrase at standard dose, 1 mL (8,500 I.U.) (one full measuring scoop or 28 drops) per meal or snack for patients up to 15 kg in body weight. 2 mL (17,000 I.U.), for a total of 4 weeks and follow patients recording stool frequency and consistency, emesis, weight, ability to advance enteral nutrition. Possible adverse effects of sucrase administration will also be recorded in addition to parental or patient perception of tolerance of feeds while on sucrase.

Give sucrase by g-tube or orally for 4 weeks

Record daily:

Stool frequency and consistency

Side effects on sucrase – blood sugar checks by finger stick and any new symptoms –
nausea, headache, etc

Emesis

Record weekly:

Ability to advance feeds

Abdominal circumference

Weight

Patient or parent perception of tolerance of feeds on sucrase by telephone questionnaire

ONE WEEK WASH OUT – no recordings

Give placebo by g-tube or orally for 4 weeks

Record daily:

Stool frequency and consistency

Side effects on sucrase – blood sugar checks by finger stick and any new symptoms –
nausea, headache, etc

Emesis

Record weekly:

Ability to advance feeds

Abdominal circumference

Weight

Patient or parent perception of tolerance of feeds on sucrase by telephone questionnaire

Possible additional tests:

Some patients will undergo blood test for genetic testing if available, those who have been scheduled for an endoscopy, for other medically indicated reasons as decided by the medical team, will have biopsies taken to rule out CSID.

Patients who consent to breath test for functional sucrase deficiency will have testing done.

Procedures:

SucraID™ (sucrase) administration:

Subject will be asked to take sucrase either orally or through g-tube with feeds daily and will be provided with this medication at no cost. Subjects will take sucrase or placebo each for 4 weeks so they will be taking additional medication daily for 8 weeks as they participate in the study.

Sucrose breath test:

This is an optional test for children over 4 years old that can cooperate by drinking a solution containing sucrose (sugar water) and breathing into a device to record components of their breath. The test will be offered free of charge to subjects in the study. This test is performed at home and the kit can be mailed back to us. The mailing costs are pre-paid. Inability to perform breath test will not eliminate subject from the study.

Endoscopy:

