Endoscopies are often performed to assess patients with short bowel syndrome with intestinal failure who are not progressing as expected. They are done to check for many things, such as, bacterial overgrowth in the intestine, inflammation in the intestine, loss of intestinal cell function, infections in the intestines etc. If a subject has had an endoscopy (obtained for clinical reasons), we will ONLY access these results for research purpose. If subject has not had an endoscopy one will only be performed if clinically indicated by medical team – we will not take additional biopsies or ask for additional tests at the time of endoscopy.

Telephone surveys:

We will conduct short telephone surveys of subject's symptoms while participating in the study. This would be similar to the phone calls they receive from the intestinal rehabilitation team about their feeds, stools, and other associated symptoms.

Medical chart review:

We will also look at recent growth chart in medical record to check growth before and during the study period, we will ask the parent or home nurse to measure abdominal circumference, weight and to check subject's blood sugars at home.

8) Outcome measures

Primary outcomes:

- Outcome Measure Title: Change in Carbohydrate Malabsorption
Outcome Measure Description: Degree of carbohydrate malabsorption will be assessed by decrease in number of stools per day.
Outcome Measure Timeframe: Baseline to Week 9
- Outcome Measure Title: Change in Carbohydrate Malabsorption
Outcome Measure Description: Degree of carbohydrate malabsorption will be assessed by change in patient symptomatology by change in score on patient symptom survey.
Outcome Measure Timeframe: Baseline to Week 9
- Outcome Measure Title: Change in Carbohydrate Malabsorption
Outcome Measure Description: Carbohydrate malabsorption will be measured by increase in growth velocity in kg/week
Outcome Measure Timeframe: Baseline to Week 9
- Outcome Measure Title: Change in Carbohydrate Malabsorption
Outcome Measure Description: Carbohydrate malabsorption will be measured by ability to advance enteral nutrition in ml/day
Outcome Measure Timeframe: Baseline to Week 9

Secondary outcomes

- Outcome Measure Title: Improved Digestion
Outcome Measure Description: Improved digestion will be measured by decreased abdominal distension/girth measured in cm
Outcome Measure Timeframe: Baseline to Week 9
- Outcome Measure Title: Improved Digestion

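### The baseline-to-Week-9 time frame given to all seven outcomes does not express the crossover's sucrase-versus-placebo comparison, and the 9-week count leaves no room for the baseline week

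*Protocol*

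**What the plan says.** **Outcomes.** In Protocol section 8 every outcome, primary and secondary, ends with "Outcome Measure Timeframe: Baseline to Week 9". Most are described as a change, a decrease or an increase. None is described as a difference between sucrase and placebo. Section 5 calls the trial a placebo-controlled crossover and justifies it by each participant acting as his or her own control.

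**Order.** Section 7 lists four weeks of sucrase, then "ONE WEEK WASH OUT – no recordings", then "Give placebo by g-tube or orally for 4 weeks". The intervention description in section 6 has the same order: sucrase, a one-week washout, and then "During cross over subjects will be administered" placebo. Randomisation appears only as a general remark in section 5b. The design figure is not shown.

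**Duration.** Section 5c says "Each subject will be enrolled for study period of 9 weeks". Sections 6 and 7 say that subjects, once enrolled, "will be observed for 1 week on their current care and we will record" the daily and weekly items. Section 7 adds that subjects take sucrase or placebo for 4 weeks each, "so they will be taking additional medication daily for 8 weeks".

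**Forms (section 6).** The sheet headed "WEEKLY RECORD (EXCEPT WASH OUT WEEK") has columns for Weeks 1–4 and 6–9, and so does the telephone questionnaire. The daily sheet has seven day columns and no week number. Vomiting is a yes/no item, the feeds row has no unit, and the questionnaire is a single unscored row on perceived tolerance.

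**The concern.** A crossover estimates a treatment effect by comparing the two treatment periods within each subject. A change from a pre-treatment week to the last week of the second period is a different quantity. It compares one period with no treatment and ignores the other period. In the written order, the period it ignores is the sucrase period.

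If section 8 is followed as worded, a real sucrase effect on stools or symptoms could be absent from the reported result, with nine weeks of intestinal adaptation or growth reported in its place. The baseline week that anchors every outcome also does not fit the stated study length, and two of the three forms have no space for it. Baseline values and emesis counts that were never recorded cannot be recovered at the analysis stage.

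**Working it through.** **1. The stated duration.** The segments are observation 1 week (sections 6 and 7), sucrase 4, washout 1 and placebo 4 (section 7).
- Without observation: 4 + 1 + 4 = 9 weeks. This reproduces the stated figure.
- With observation: 1 + 4 + 1 + 4 = 10 weeks. This does not.

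**2. Which week is baseline?**
- Observation as Week 0: sucrase Weeks 1–4, washout Week 5, placebo Weeks 6–9. This matches the forms.
- Observation as Week 1: sucrase Weeks 2–5, washout Week 6, placebo Weeks 7–10. The forms would skip a sucrase week (5), record the washout week (6) and have no Week 10.

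Under either numbering Week 9 is a placebo week in the written order. The remaining steps use Week 0 for observation.

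**3. Level outcomes** (stools, symptom score, emesis, consistency, girth). Assume y(t) = a + b·t + d while on sucrase, with no carryover and no placebo response.
- Written order: y(9) − y(0) = 9b + 0d.
- Reverse order: y(9) − y(0) = 9b + d.

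If both orders are used, d is the difference between the two sequence groups. That is a between-subject comparison and not the within-subject one that section 5b relies on. For illustration only, with assumed d = −2 stools/day and b from 0 to −0.2 per week, the literal change in the written order is 0 to 9 × (−0.2) = −1.8, all of it trend.

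**4. Accumulating outcomes.** Assume a background gain g per week, an extra gain c per sucrase week, and gains that are kept.
- Enteral volume: V(9) − V(0) = 9g + 4c in either order.
- Growth velocity over the whole window: (W(9) − W(0))/9 = g + 4c/9 in either order.

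Both contain some sucrase effect. Because the result is the same whichever treatment came first, neither separates sucrase from placebo, even between sequences.

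**5. The period contrast instead.** The mean week is 2.5 for Weeks 1–4 and 7.5 for Weeks 6–9. For a level outcome, sucrase minus placebo is:
- written order: d − 5b
- reverse order: d + 5b
- balanced orders: d

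**6. Enteral volume needs one chosen summary.** For a retained gain, the contrast of within-period slopes is c in either order. The contrast of period means is −5g − 1.5c in the written order, 5g + 2.5c in the reverse order, and 0.5c when balanced. For a step that reverts in the washout, the slope contrast has coefficient 0 on d, while the period-mean contrast is d − 5b (written) or d (balanced). The two summaries can therefore disagree.

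**7. Precision of weight slopes.** Four weekly records give Sxx = 2.25 + 0.25 + 0.25 + 2.25 = 5 per period. With independent weighing errors of SD s, the slope difference has variance 2s²/5 = 0.40s², so its SD is 0.63s.

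**8. Forms against outcomes.**
- Emesis is defined as a daily count; the form has yes/no.
- Enteral nutrition is defined in ml/day; the form gives no unit.
- The symptom outcome is a survey score; the questionnaire has no score.
- Feeds, girth, weight and symptom score (four outcomes, three of them primary) have no observation-week column, although sections 6 and 7 ask for these items in that week.

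**The case against.** The strongest reply is that the time frame is a template field marking the window over which data are collected. Section 8 does not state a Week 9 minus baseline subtraction, both periods are recorded daily and weekly, and the contrast may be set out in an analysis plan that is not shown. This is plausible, and for that reason the result in step 3 is conditional on a literal reading. It does not remove the point: the outcomes are worded as changes under that time frame, and nothing in section 8 ties them to the own-control comparison.

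The order may also be randomised, since section 5b mentions randomisation and the figure is missing. That stands too. It changes 9b to 9b + d for some subjects, but does not turn the change into a within-subject treatment comparison.

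Two stronger inferences are tempting and not supported:
- **That baseline has no place on any form.** The daily sheet carries no week number and can serve the observation week for stools, consistency and vomiting. Section 7 also provides for chart review of growth before and during the study. Only the weekly and telephone forms lack the column.
- **That a sucrase effect on growth velocity would vanish.** It vanishes in the written order only if velocity is taken from the last two weights, W(9) − W(8). The protocol does not specify that. Over the whole window the effect is diluted to 4c/9.

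The week count may be largely a matter of numbering, and no sample-size figure depends on it. Even so, 9 weeks from enrolment and a 1-week observation after enrolment cannot both hold with 4 + 1 + 4.

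**Conclusion.** The point holds as a defect of definition. As worded, the time frame does not express a sucrase-versus-placebo comparison for any of the seven outcomes. For the five level outcomes, the literal change in the written order contains none of d; with mixed orders, d is recoverable only between sequences. For enteral volume and whole-window growth velocity, the treatments are not separated in either order. These results assume a linear trend, no carryover, no placebo response and, for the accumulating outcomes, retained gains.

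The conflict of 9 against 10 weeks and the mismatches between forms and outcomes are plain on the text and need no model.

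A reader might go further and conclude that the trial cannot measure the sucrase effect. The documents do not support that: both periods are recorded, so a period contrast is available once it is stated. This should be fixed. Confidence is medium, because the intended meaning of the time frame and the intended order cannot be seen.

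**What to change.** - **Section 8:** state each outcome as the within-subject sucrase-minus-placebo difference between Weeks 1–4 and Weeks 6–9. Use period means for stools, emesis, consistency, symptom score and girth, and the within-period rate of gain (kg/week) for weight. For enteral volume (ml/day), choose one summary in advance in the light of step 6. If the present time frame is only the collection window, say so.
- **Week count:** label the observation week (Week 0 fits the forms) and reconcile section 5c with sections 6 and 7.
- **Forms:** add an observation-week column to the weekly record and the telephone questionnaire. Record emesis as a count, feeds in ml/day, and symptoms on a scored survey.

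The cost is a rewording of section 8, small form changes and slightly more recording. Weight slopes will rest on four weekly records per period (SD 0.63s for the difference). If the order is fixed as written, the contrast remains confounded with time (d − 5b). That is a separate issue, which this change does not solve.

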Title page:

Protocol Title: Functional sucrase deficiency in short bowel syndrome patients with intestinal failure

eProst Number: 20191253
Protocol Version Number: 2
Protocol Version Date: 2/6/2020
PI Name: [name]
NCT Number: NCT04604275

1) Protocol Title

Functional sucrase deficiency in short bowel syndrome patients with intestinal failure

2) Objectives

Primary Aim:

To determine if sucrase supplementation in intestinal failure resulting from short gut syndrome will improve carbohydrate malabsorption, reducing symptoms such as bloating, diarrhea and abdominal pain and thus improve patient's ability to advance enteral nutrition in short gut syndrome patients.

Secondary aim:

To determine if reduced bowel mass/length that occurs in short gut syndrome results in decreased functional sucrase levels and thus disaccharide malabsorption causing symptoms such as bloating, diarrhea and abdominal pain and/or resulting in inability to advance enteral nutrition.

3) Background

Short gut syndrome patients have decreased production of disaccharidases, like sucrase, due to loss of enterocyte mass and thus these patients cannot digest sucrose fully.

The resulting maldigestion of sucrose causes abdominal distension, vomiting and diarrhea that limits the advancement of enteral nutrition in short gut syndrome patients with intestinal failure

The administration of exogenous sucrase will improve sucrose digestion and thus the advancement of enteral nutrition in short gut syndrome patients with intestinal failure.

Sucrose digestion:

Carbohydrates in the diet provide the major exogenous source for glucose, which is the primary energy source for cells. They account for 40-60% of the calories in the western diet and higher percentages in protein scarce diets.

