Outcome Measure Description: Improved digestion will be assessed by number of emesis per day
Outcome Measure Timeframe: Baseline to Week 9
- Outcome Measure Title: Improved Digestion
Outcome Measure Description: Improved digestion will be assessed by change in stool consistency from hard to formed to semi solid to liquid with pieces to only liquid observed daily
Outcome Measure Timeframe: Baseline to Week 9

9) Adverse Events

a) Definition of AEs

Reported adverse events are minor and rare with Sucraid (sucrase) and overdose has not been described. In clinical studies the adverse experiences were as follows: abdominal pain, vomiting, nausea, diarrhea, constipation, insomnia, headache, nervousness, and dehydration.

b) Definition of SAEs

In one study, one asthmatic child experienced a serious hypersensitivity reaction (wheezing) probably related to sacrosidase. The event resulted in withdrawal of the patient from the trial but resolved with no sequelae.

c) Time Period and Frequency for AE assessment and Follow-up

During weekly phone calls we will assess for worsening symptoms, including but not limited to the AE as listed above

d) Adverse Event Reporting

All adverse events as defined by the FDA will be recorded by study team and reported in the results section of the study and publications.

e) Serious Adverse Event Reporting

All adverse events as defined by the FDA will be recorded by study team and reported in the results section of the study and publications. Subjects will be withdrawn as necessary if SAE occurs during study period.

10) Data and Specimen Banking

Data will be kept on a secure drive and only be accessed by the study team members. Data will be de-identified prior to data entry.

Specimens taken for pathology (for other medically indicated reasons) will be kept in patients private medical record as usual.

11) Data Management

Statistics will be done in compliance with HIPAA regulations on de-identified data.

Data will be stored on a secure drive and only accessible to study team members during and after the study.

Data will be kept post collection in compliance with regulations.

12) Risks to Subjects

Sucrase may cause a serious allergic reaction.

Blood glucose levels may change after taking sucrase – each patient already has monitor to check daily sugars while on therapy.

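### A secondary outcome counts vomiting episodes per day, but the protocol's printed daily record collects vomiting only as yes or no

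*Protocol*

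**What the plan says.** **Emesis.** Section 8 lists among the secondary outcomes: "Improved digestion will be assessed by number of emesis per day". The recording lists in sections 6 and 7 name emesis as a daily item, separate from side effects, without a unit. The daily record printed in section 6 has one row for it, "VOMITING (YES/NO", placed with the headache, nausea and abdominal pain ticks after the row "SUCRASE SIDE EFFECTS". The stool frequency row on the same record carries no yes/no tag.

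**Telephone item.** The printed telephone questionnaire in section 6 has a single row, "Patient or parent perception of tolerance of feed on sucrase", with columns for weeks 1 to 4 and 6 to 9. No response options are printed.

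**Symptom score.** One of the four primary outcomes in section 8 is "change in patient symptomatology by change in score on patient symptom survey". Section 7 describes the telephone surveys as "similar to the phone calls they receive from the intestinal rehabilitation team about their feeds, stools, and other associated symptoms". Section 9 c) adds that the weekly calls look for worsening symptoms, including the listed adverse events. None of these places names a scored instrument.

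**The concern.** An outcome can be no finer than the field that collects it. A fall from 4 episodes a day to 2, or from 2 to 1, is recorded as yes before and yes after. An analysis plan can later redefine the outcome as days with vomiting, but it cannot rebuild counts that were never written down. In a crossover with 10 subjects (section 20), information lost at recording is hard to make up.

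The telephone wording raises a lesser concern. A question about tolerance while on sucrase does not fit the weeks when the subject takes placebo. The symptom score raises a question of identification: the reader cannot tell which set of questions produces it.

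**Working it through.** The protocol states no figure on this point, so there is none to reproduce. The first step compares the texts. The second puts a range on the loss.

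**Step 1: outcome against form**

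| Item | Section 8 asks for | Printed record gives |
|---|---|---|
| Stools | number per day | stool frequency, no yes/no tag |
| Emesis | number per day | vomiting, yes/no |

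The form therefore treats a frequency and a tick differently, and vomiting is a tick. The recording lists add the word emesis but no unit and no further field. Section 6 b) uses home nursing records only to check compliance. Seven yes/no cells give between 0 and 7 vomiting days per week and nothing about episodes within a day.

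**Step 2: size of the loss under assumptions**

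Input from the protocol: 4 weeks of treatment per period, which is 28 days. Assumed, because the protocol gives no vomiting rate: a Poisson daily count with mean λ, independent days, and a true 50% fall.

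- Chance of a yes-day: p = 1 − exp(−λ). Expected yes-days = 28p.
- Information on log λ from one day's count: λ.
- Information from one yes/no day: (λe^(−λ))² / [p(1 − p)] = λ² / (e^λ − 1).
- Share kept by yes/no: λ / (e^λ − 1).

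| λ per day, before → after | Episodes in 28 days | Yes-days in 28 days | Fall in yes-days | Share kept at starting λ | Equivalent days of counts |
|---|---|---|---|---|---|
| 3 → 1.5 | 84 → 42 | 28 × 0.950 = 26.6 → 28 × 0.777 = 21.8 | 18% | 3/19.09 = 0.157 | 4.4 |
| 1 → 0.5 | 28 → 14 | 28 × 0.632 = 17.7 → 28 × 0.393 = 11.0 | 38% | 1/1.718 = 0.582 | 16.3 |
| 0.2 → 0.1 | 5.6 → 2.8 | 28 × 0.181 = 5.1 → 28 × 0.095 = 2.7 | 48% | 0.2/0.2214 = 0.903 | 25.3 |

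Sensitivity: with overdispersed counts (negative binomial, variance μ + μ²/k, k known), the share kept for k = 1 is 1/(1 + μ). That is 0.25, 0.50 and 0.83 at 3, 1 and 0.2 per day. For k = 0.5 it is 0.26, 0.46 and 0.78. The pattern is the same: a large loss when vomiting is frequent and a small one when it is rare.

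**Step 3: telephone item**

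The questionnaire columns omit week 5, and the weekly record with the same weeks is headed as leaving out the wash-out week. Read that way, one block of columns belongs to sucrase and the other to placebo, whatever the order. The same sucrase wording therefore stands over weeks on placebo. The recording list for the placebo period in section 7 repeats it.

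**The case against.** The strongest reply on emesis is that the yes/no row may be only the safety tick. It follows the side-effects row, while the recording lists name emesis as an item of its own. The protocol never says that the printed grid is the whole of data capture, and section 21 refers to REDCap, whose fields are not shown. This stands as a limit. A reader might infer that the outcome cannot be produced at all, or that counts will certainly be lost; the document does not show that. It does not remove the conflict, because no count field appears in any form or text at hand.

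The loss figures are also open to challenge. The rates, the 50% fall and the distributions are assumed, and days are treated as independent. With 10 subjects, variation between subjects in response could dominate the error, so the loss for the treatment contrast could be smaller than the per-day shares suggest. That is fair: the figures give a range and do not show a large effect.

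On the symptom score, a reader might infer that a primary outcome has no instrument behind it. The document does not support so much. Sections 7 and 9 c) describe calls that cover far more than the one printed row, and a call script may exist outside the protocol. What is left is missing detail.

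A reader might also hold it against the plan that bloating has no row. The aim reads "reducing symptoms such as bloating, diarrhea and abdominal pain", and its list is illustrative. Bloating is not itself an outcome in section 8, and distension has its own measure: "Improved digestion will be measured by decreased abdominal distension/girth measured in cm". That is not a defect.

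Finally, one might infer that the sucrase wording biases the answers. Bias is possible, but nothing in the document shows it.

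**Conclusion.** The conflict between the emesis outcome and the daily record holds. It concerns one of three secondary outcomes. If the printed record is the source, the trial can report vomiting days but not episodes per day, and later analysis cannot repair this. Under the assumed Poisson model, the information kept runs from about 90% at 0.2 episodes per day to about 16% at 3 per day. Which end applies cannot be known from the protocol. The conclusion rests on the printed record being the source of the outcome, which is the natural reading but is not stated.

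The telephone wording is a secondary point that should be corrected without any claim of bias. The symptom score needs clarification only. The correction is worth making because it is cheap, not because a large loss has been shown.

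**What to change.** **Main change.** On the daily record, replace the yes/no vomiting row with the number of vomiting episodes that day, with 0 entered when there are none. The cost is a daily count instead of a tick, with no extra visit or procedure. Alternatively, keep the tick and restate the outcome in section 8 as days with vomiting. That costs nothing in collection but gives up the episode count. If REDCap already holds a daily count, say so in the protocol and name that field as the source.

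**Wording.** In the telephone item and the recording lists, replace the reference to sucrase with a neutral term such as study product, identical in both treatment periods.

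**Clarification.** State which questionnaire yields the symptom survey score and give its response scale. If it is the telephone questionnaire, list the items that are scored. These two changes are text edits to the forms and the protocol.
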